# 5. INTRODUCTION

## 5.1. Background

In the context of improved survival from HIV infection itself, COPD (chronic obstructive pulmonary disease; a form of lung disease that includes emphysema, which makes breathing difficult) is emerging as an important cause of morbidity and perhaps ultimately mortality in this population. HIV-infected patients are at increased risk of COPD, likely due to multiple factors, including an increased presence of smoking, chronic inflammation and progression of immunodeficiency, oxidant stress (excessive levels of natural chemicals called oxidants and free radicals that can damage tissue), and respiratory infections. While natural history data on COPD are limited in the era of potent antiretroviral therapy, earlier data suggest that the course of emphysema may be accelerated in this population. Our preliminary data suggest that several matrix metalloproteinases (MMPs) derived from alveolar macrophages (a type of immune cell found in the lungs) have an increased cellular response in HIV-infected smokers, which could contribute to accelerated emphysema. MMPs are enzymes that break down the structural support of tissues, including the airways in the lung.

Based on these observations, we hypothesize that pharmacologic inhibition of MMPs by doxycycline will favorably modify the natural history of COPD in HIV-infected patients. To test

this hypothesis, we propose conducting a proof of concept pilot study as a prelude to a possible phase II randomized, placebo-controlled trial of doxycycline for COPD in HIV-infected patients should the proof of concept be successful. Our research team, led by a pulmonologist/researcher with expertise in HIV-associated COPD and an infectious diseases specialist/clinical trials expert, is well positioned to propose such a trial to the NIH-funded AIDS Clinical Trials Group (ACTG).

## 5.2. Rationale for Study

Our proposed study of doxycycline in HIV-infected subjects with COPD is highly innovative. There are very limited clinical data on the use of doxycycline for COPD in the general population, and there are no adequately controlled studies. Our pilot study will not only serve as the basis for designing a phase II trial but also will provide a unique opportunity to advance our scientific understanding of the biological and physiological effects of MMP inhibition in lung tissue. No study, to our knowledge, has evaluated the effects of doxycycline on MMPs and proinflammatory cytokines in the lung in humans. Our approach to use bronchoalveolar lavage to quantify the biological effects of doxycycline on MMP and cytokine gene and protein expression is novel and will advance knowledge significantly in this field. By correlating these biological effects with drug levels in epithelial lining fluid (ELF), alveolar macrophages (AM) and serum and changes in pulmonary function, we will be able to characterize the pharmacokinetic and pharmacodynamic profile of doxycycline in HIV-infected subjects with COPD.

**Controlled HIV infection.** We are requiring a CD4 count > 200 cells/mm3 and HIV RNA < 400 copies/ml to select for a patient population that is at low risk of pulmonary opportunistic infections.

This will also minimize any confounding factors related to large scale changes in CD4, reconstitution syndrome, etc that might occur in a cohort with higher viral loads who have more recently been initiated on antiretroviral therapy.

**COPD definition -** We will exclude advanced COPD (GOLD III/IV) in this proof of concept study in order to minimize risk to subjects from the bronchoscopies. We anticipate including more advanced COPD in a Phase II study, which will not necessarily include mandatory bronchoscopies. Since HIV+ smokers can have emphysema with a low number of pack-yr we will accept anyone with > 3 pack year history. We did not include a 2nd CT in the study design, because the time frame is too short to expect to see any favorable radiographic effects on preserving lung parenchyma to justify the additional radiation exposure.

# 5.3 Preliminary Studies

**MMPs in HIV+ Subjects with Emphysema.** [name] has recently published on the pattern of increased MMP expression in HIV+ individuals with emphysema RNA was successfully isolated from alveolar macrophages of HIV+ individuals with emphysema (and microarray data was deposited in GEO) and gene expression studies were performed and compared with the results of gelatinase assays and Western blots. These studies showed increased amounts and activation of MMP-2, -7, -9 and -12 in the epithelial lining fluid of HIV+ individuals with emphysema. Using a pan-MMP activity assay, 8/8 HIV+ subjects with emphysema had detectable MMP activity in ELF (data not shown). Further studies have addressed the potential

upstream cytokine regulation of MMPs by cytokines. Comparing the cytokine protein profile in ELF, HIV+ individuals, both smoking and nonsmoking show a broad spectrum expression of cytokines, that shares similarities with HIV negative individuals with emphysema, but not with HIV-negative nonsmokers and smokers with normal lung function. Interestingly, several of the cytokines identified are important in the Th17 pathway. Preliminary data further indicate that IL-23 (among other cytokines) upregulates human alveolar macrophage MMP-9 production via an intermediate step that involves T-lymphocytes (manuscript in preparation). These studies, along with the developing literature around the putative role of MMPs in the development of COPD and emphysema, provide a biologic rationale for the current proposal to test an MMP inhibitor in an effort to slow the progression of COPD and emphysema.

**Pulmonary Function in HIV+ Subjects with COPD/Emphysema.** In 2011, the Department of Genetic Medicine COPD human samples research core headed by [name] performed 355 research bronchoscopies and the group has successfully performed thousands of research bronchoscopies over the last 15 years. In addition, the human samples core has independently (of [name] group) screened 262 HIV-infected current or ex-smokers for a COPD study, of whom 34 (13.0%) met the PFT criteria for this study (post-bronchodilator FEV1/FVC < 0.7 and/or DLCO < 80% predicted).

These individuals came for screening to volunteer for a research bronchoscopy. Specifically, 23 (68%) of 34 had post-bronchodilator FEV1/FVC < 0.7 and 26 (76%) had DLCO < 80%.

# 6. TRIAL OBJECTIVES AND PURPOSE

#### 6.1. Primary Objectives

• To determine the safety and tolerability of twice daily doxycycline for 6 months in HIV-infected subjects with COPD and/or emphysema.

## **Secondary Objectives:**

- To characterize changes in FEV1, FVC, FEV1/FVC, DLCO over time
- To characterizes change in respiratory symptoms over time (using the CAT COPD assessment test)
- To characterize change in BAL absolute cell number (AM, PMN, lymph)
- To characterize change in AM gene expression of MMPs and cytokines
- To characterize change in BAL fluid MMP enzyme activity and cytokine levels
- To characterize change in serum inflammatory markers (hsCRP, sIL-6, TNF-α, IL-1β, procalcitonin)
- To determine doxycycline drug concentrations in serum, AM and ELF
- To characterize change in quantitative bacterial burden in BAL fluid
- To characterize frequency of doxycycline-resistant bacteria
- To describe adherence to study therapy by self-report and pill counts
- To determine the incidence of non-elective hospitalization, classified as respiratory or non-respiratory

• To determine the incidence of acute exacerbation of COPD (using the GOLD definition of change in symptoms requiring medication [we will use systemic steroids and/or antibiotics as the indicators])

## 7. INVESTIGATIONAL PLAN

#### 7.1. Endpoints

The primary endpoint will be safety/tolerability, and secondary endpoints will include change in pulmonary function (FEV1) by spirometry, inhibition of MMP activity in a pan-MMP activity assay as well as individual MMPs assessed by gelatinase assays and doxycycline levels in serum, epithelial lining fluid and bronchoalveolar lavage cell pellets (consisting of alveolar macrophages, lymphocytes and some neutrophils).

#### 7.2. Overall Study Design and Plan: Schedule of Assessments

#### SCREENING

- Physical examination including vital signs (blood pressure, pulse, and breathing rate) weight and height, and amount of oxygen in the blood
- Lung function tests (lung volumes, spirometry (post-bronchodilator) and diffusing capacity of the lung for carbon monoxide [DLCO])
- Blood will be drawn from a vein to check blood counts (to look for infection or anemia), HIV viral load (amount of virus in the blood), CD4 (T-cell) count, and blood chemistries (blood minerals, blood sugar level, kidney and liver function, PT/PTT, complete blood count, electrolytes, renal function, CMP, CBC+diff, c-reactive and carboxy hemoglobin). If documentation of an HIV test result is not available, we will do an HIV test at screening.
- Urine will be collected to measure protein levels, check kidney function, measure poisonous alkaloid from tobacco, the break-down product of nicotine from cigarette smoke, PGE collection and to evaluate toxicology for drugs
- For females capable of getting pregnant, urine will be collected to test for pregnancy. If you are pregnant, you will not be allowed to participate in this study
- Electrocardiogram, a non-invasive test that provides a tracing of the heart's electrical activity

## **PRE-ENROLLMENT (OPTIONAL)**

- Physical examination including your signs (blood pressure, pulse, and breathing rate) weight and height, and amount of oxygen in the blood
- Blood will be drawn from a vein to check blood counts (to look for infection or anemia), HIV viral load (amount of virus in the blood), CD4 (T-cell) count, and blood chemistries (blood minerals, blood sugar level, kidney and liver function, PT/PTT, complete blood count, electrolytes, renal function, CMP, CBC+diff, c-reactive and carboxy hemoglobin). If documentation of an HIV test result is not available, we will do an HIV test at screening.
- For females capable of getting pregnant, urine will be collected to test for pregnancy. If you are pregnant, you will not be allowed to participate in this study
- A detailed x-ray of the lungs (High-resolution Computed Tomography, or HRCT) will be done if a scan of good quality was not done in the past 6 months

#### ENROLLMENT

- Physical examination including your signs (blood pressure, pulse, and breathing rate) weight and height, and amount of oxygen in the blood
- Lung function tests (lung volumes, spirometry (post bronchodilator))
- Assessment of any side effects or symptoms and if there have been any changes in any of the medications you may be taking
- EKG (optional; repeated only if 30 days have passed since last EKG)
- Blood will be drawn from a vein to check blood counts (to look for infection or anemia), blood chemistries (blood minerals, blood sugar level, kidney and liver function), stored serum and biomarkers
- Urine will be collected to evaluate toxicology for drugs
- Urine will be collected to measure poisonous alkaloid from tobacco and the break-down product of nicotine from cigarette smoke
- For females capable of getting pregnant, urine will be collected to test for pregnancy. If you are pregnant, you will not be allowed to participate in this study
- Study drug dispensing
- Respiratory symptom and smoking questionnaires
- Oral rinse to collect samples of the bacterial communities in the oral mouth and upper airway and to remove loose debris that may contaminate the airway samples.
- Bronchoscopy

#### WEEK 2

- Physical examination including your signs (blood pressure, pulse, and breathing rate) weight and height, and amount of oxygen in the blood
- Lung function tests (lung volumes, spirometry (post bronchodilator) and diffusing capacity of the lung for carbon monoxide [DLCO])
- Assessment of any side effects or symptoms and if there have been any changes in any of the medications you may be taking
- Blood will be drawn from a vein to check blood counts (to look for infection or anemia), blood chemistries (blood minerals, blood sugar level, kidney and liver function), stored serum and biomarkers
- For females capable of getting pregnant, urine will be collected to test for pregnancy. If you are pregnant, you will not be allowed to participate in this study

#### WEEK 6

- Physical examination including your signs (blood pressure, pulse, and breathing rate) weight and height, and amount of oxygen in the blood
- Assessment of any side effects or symptoms and if there have been any changes in any of the medications you may be taking
- Blood will be drawn from a vein to check blood counts (to look for infection or anemia), blood chemistries (blood minerals, blood sugar level, kidney and liver function), stored serum and biomarkers
- For females capable of getting pregnant, urine will be collected to test for pregnancy. If you are pregnant, you will not be allowed to participate in this study

• Study drug dispensing

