Data will be entered into the REDCap, a PHP-based system developed by Vanderbilt University and currently managed and updated through a national consortium that includes the Weill Cornell CTSC. In collaboration with the CTSC's data management group, we will create a secure, HIPAA-compliant, web-based study-specific database system with customized full field validation capabilities, a full audit trail and user-based privileges.

We will compute summary statistics (e.g. mean, median, SD, interquartile range, minimum and maximum) for demographic/clinical variables and the primary outcome data (e.g. spirometry endpoints, adverse events, biological endpoints, measurable doxycycline levels in serum and

ELF) by study arm. We will compare changes from baseline in continuous variables between the two groups by 2-sample t-tests or the non-parametric Wilcoxon's rank sum test as appropriate. We will perform repeated measures ANOVA or Multivariate ANOVA for repeated measures data (e.g. spirometry) as deemed appropriate after checking assumptions of sphericity using Mauchly's Test. Given the moderate sample size for this data we will compute confidence interval for estimates from RMANOVA or MANOVA to assess their precision. The proportions of subjects in each arm experiencing adverse events will be summarized by grade and compared by Chi-squared or Fisher's exact tests or generalized Fisher's test (using Monte Carlo approximations) as appropriate. In a pre-specified subgroup analysis, we will explore whether the subset of subjects with emphysema by CT respond differently to doxycycline compared to those without emphysema.

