#### Weill Cornell Doxycycline for COPD in HIV-Infected Patients

#### Table I: Schedule of Evaluations

	SCREENING	PRE-ENTRY	ENTRY	WK	WK	WK 11	WK	WK 18	WK 24	PREMATURE
		(OPTIONAL)		2	6	(OPTIONAL)	12			DISCONTINUATION
Informed consent, medical	Х									
history										
Clinical Assessments 	Х	Х	$X^*$	Х	Х	Х	$X^*$	Х	Х	Х
Safety labs 	X	Х	$X^*$	Х	Х	Х	$X^*$	Х	Х	Х
Blood test 	X	Х	X*			Х	$X^*$			
Other labs 	X									
HIV viral load	Х						Х		Х	Х
CD4 (T-cell) count	Х						Х		Х	Х
Research blood (collection priority) 			Х	Х	Х		Х	Х	Х	
Pregnancy test (urine)	X	Х	Х	Х	Х		Х	Х	Х	
Urine toxicology (drug panel)	Х		Х				Х			
PGE urine collection 	X**						X**			
Urinanalysis 	Х									
Urine Metabolites 	X		Х				Х	Х		
Spirometry	X		Х				Х		Х	Х
EKG	X		Х				Х			
Bronchoscopy 			Х				Х			
High resolution chest CT 		Х	X*							
Oral rinse 			Х				Х			
Respiratory (CAT)/smoking questionnaires			Х		Х		Х		Х	Х
Dispense study drug			Х		Х		Х	Х		
Pill count/adherence questionnaire				X	Х		Х	X	Х	X

\* Optional procedures if procedures were already conducted during the optional visits.

 Clinical assessments include full physical examination at screening, targeted physical examinations at other visits, ongoing assessments for adverse events and new clinical diagnoses and CAT review at each visit.

 Safety labs consist of complete metabolic panel, complete blood count, electrolytes, liver function and renal function (CMP, CBC+diff, c-reactive, carboxy hemoglobin).
  PT/PTT blood test

 Other Labs (Hepatitis panel (A, B and C), alpha-1 anti-trypsin, IgE)

Weill Cornell	Investigational New Drug Application
Doxycycline for COPD in HIV-Infected Patients	Clinical Protocol

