# 9. STUDY CONDUCT

#### 9.1. Study Overview

A subject's participation in this study is expected to be approximately 24 weeks. The day the subject begins taking the doxycycline will be designated as day 0 and enrollment. The study will include a bronchoscopy procedure at the enrollment/entry visit and week 12 visit.

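### Two pre-treatment spirometries are scheduled, but the lung-function comparison does not say which one is baseline or whether both are used

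*Combined protocol and SAP*

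**What the plan says.** - **Screening (section 7.2):** "Lung function tests (lung volumes, spirometry (post-bronchodilator) and diffusing capacity of the lung for carbon monoxide [DLCO".
- **Enrollment (section 7.2):** "Lung function tests (lung volumes, spirometry (post bronchodilator", with no DLCO listed. Dispensing comes later in the same list.
- **Table I:** spirometry is marked at Screening, Entry, week 12, week 24 and premature discontinuation. The Entry mark has no asterisk, so the test is not optional.
- **Section 9.1:** "The day the subject begins taking the doxycycline will be designated as day 0 and enrollment". With the order of the Enrollment list, this makes the Entry test pre-dose by implication. No sentence says so.
- **Synopsis, Statistical Considerations:** "We will compare changes from baseline in continuous variables between the two groups by 2-sample t-tests or the non-parametric Wilcoxon's rank sum test as appropriate". A second analysis follows: "We will perform repeated measures ANOVA or Multivariate ANOVA for repeated measures data (e.g. spirometry) as deemed appropriate". Neither sentence says which visits supply the baseline or enter the model.
- **Use of the word baseline:** the Synopsis ties it to a visit only for bronchoscopy. Section 10 has Screening and baseline together in its title.
- **Table II:** no window is set between Screening and Entry.

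**The concern.** Change in FEV1 is the first secondary endpoint named in section 7.1, and section 11 calls the pulmonary function test the primary measure of efficacy. With 20 versus 10 subjects, precision is scarce, and noise in a single baseline test passes in full into every change score. A second pre-treatment test is already being collected and could remove part of that noise.

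Separately, an undefined baseline leaves the analyst free to take Screening, Entry, their mean or the better of the two. That choice should be fixed before the data are unblinded, whatever the size of the precision gain.

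**Working it through.** **The plan's own figure.** The only power statement concerns grade 2 or higher toxicity. With 20 doxycycline recipients and a rule of at most 5 events, exact binomial power at a true rate of 20% is 0.804 and alpha at 45.5% is 0.0505. This reproduces the stated 80%. No figure is given for lung function.

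**Inputs.** 20 versus 10 subjects (Synopsis). Correlations and SDs are assumptions, because the documents give none. Let S, E and F be the Screening, Entry and follow-up values, with common variance 1.

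**Formulas**
- Change from Entry alone: 2 - 2r(E,F).
- Change from the mean of S and E: 1 + (1 + r(S,E))/2 - r(S,F) - r(E,F).
- ANCOVA residual, Entry as covariate: 1 - r(E,F)².
- ANCOVA residual, both as covariates: 1 - c'R⁻¹c, where c = (r(S,F), r(E,F)) and R is the correlation matrix of S and E.

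**Equal correlation r.** Change variance goes from 2(1 - r) to 1.5(1 - r): ratio 0.75, SE ratio √0.75 = 0.866. The ANCOVA residual goes from 1 - r² to 1 - 2r²/(1 + r), a cut of 19.8%, 22.4% and 23.7% at r = 0.80, 0.90 and 0.95. For an assumed within-subject SD of 0.15 L, the 95% half-width falls from 2.048 × 0.15 × √2 × √(1/20 + 1/10) = 0.168 L to 0.146 L.

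**Other correlation patterns.** Ratios compare with Entry alone. Power is for a difference of 0.9 SD of change from Entry (t-test, 28 df, two-sided 0.05); using Entry alone it is 0.61.

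| r(S,F) | r(E,F) | r(S,E) | Change: mean / Entry | Power with mean | ANCOVA: both / Entry |
|---|---|---|---|---|---|
| 0.90 | 0.90 | 0.90 | 0.15/0.20 = 0.75 | 0.74 | 0.776 |
| 0.90 | 0.90 | 0.95 | 0.175/0.20 = 0.875 | 0.67 | 0.891 |
| 0.90 | 0.90 | 0.98 | 0.19/0.20 = 0.95 | 0.63 | 0.957 |
| 0.85 | 0.90 | 0.90 | 0.20/0.20 = 1.00 | 0.61 | 0.956 |
| 0.85 | 0.90 | 0.95 | 0.225/0.20 = 1.125 | 0.56 | 0.999 |
| 0.80 | 0.90 | 0.90 | 0.25/0.20 = 1.25 | 0.52 | 0.997 |

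In the last row, change from Screening alone has variance 2 - 1.6 = 0.40, twice that from Entry. The unstated choice of visit can therefore matter more than averaging. Using the mean as a single covariate in that row also loses (ratio 1.26).

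**Decaying correlation.** Take correlation = R × d^weeks, with assumed R = 0.93 to 0.97, d = 0.996 to 0.999 per week, a Screening-to-Entry gap of 2 to 12 weeks, and follow-up at week 24.
- Best case (R = 0.93, d = 0.999, gap 2): r(E,F) = 0.908, r(S,F) = 0.906, r(S,E) = 0.928; ratio 0.150/0.184 = 0.81.
- Worst case (R = 0.97, d = 0.996, gap 12): 0.881, 0.840, 0.924; ratio 0.2415/0.2379 = 1.02.

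Most combinations fall between 0.80 and 0.95, a cut of about 5-20%. Entering both values as covariates did not raise residual variance in any case tried.

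**Price of the second covariate.** For k normally distributed covariates and N = 30 in two arms, the expected variance of the contrast is multiplied by (N - 3)/(N - 3 - k): 27/26 for one, 27/25 for two. The second covariate costs 26/25 = 1.04, about 2% in SE.

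**The case against.** The strongest reply is that the plan does not commit to a single baseline. It is silent, and the repeated-measures analysis named for spirometry could include both pre-dose visits. This stands: a reader might infer that the plan discards one test, but the documents show only that its use is unspecified.

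A second tempting inference is a 25% variance cut at any correlation, equal to 30/0.75 = 40 subjects, with power rising from 61% to 74%. The arithmetic is right, but only if every pair of visits is equally correlated, and the 0.9 SD effect is not in the documents. The plan also points to gaps that may be long. Table II sets no limit, an optional pre-entry visit may intervene, and the EKG is repeated at Enrollment only if 30 days have passed. With a stale Screening value the simple mean can lose, so averaging is not a free gain.

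Third, Screening FEV1/FVC may also decide eligibility. Regression to the mean then affects within-arm change, which the secondary objective to describe changes over time includes. Using Entry alone is therefore defensible for descriptive change. The between-arm contrast is protected by randomization.

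Finally, this is a pilot with a safety primary endpoint, and no primary conclusion depends on the point. That limits its weight but does not remove it.

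**Conclusion.** The point holds as a cheap improvement. Two mandatory pre-treatment spirometries are scheduled, baseline is undefined, and the stated between-arm test of change is unadjusted. Using both values would cut change-score variance by 25% under equal correlations and more plausibly by about 5-20%. These sizes rest on assumed correlations and on the Entry test preceding the first dose.

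The simple mean can gain nothing or lose if Screening is old. Two covariates should not lose beyond the one degree of freedom, roughly 4% of variance at N = 30. That price would absorb most of the gain when the two tests are nearly redundant (third row of the table).

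The point covers FEV1, FVC and FEV1/FVC only. DLCO is not listed at Enrollment, and the primary safety analysis is unaffected.

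**What to change.** Before unblinding, add a short paragraph to the analysis plan:

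1. Compare FEV1, FVC and FEV1/FVC between arms by ANCOVA, or a mixed model, with both the Screening and Entry post-bronchodilator values as covariates.
2. If a change score is reported, take it from the mean of the two values when they were taken close together, with the maximum interval stated in advance, and otherwise from Entry.
3. If only one valid pre-dose value exists, use that one.
4. State that Entry spirometry precedes the first dose and the bronchoscopy, and record the Screening-to-Entry interval.
5. Note that within-arm changes need care because the Screening value may also determine eligibility.

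List the follow-up visits in the model at the same time. Section 7.2 includes spirometry at week 2 and Table I does not, so the two must be reconciled.

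No new visit, test or subject is needed. The cost is one degree of freedom and slightly more analysis work.
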